- Combined [REDACTED] pharmacokinetic, and efficacy data show a trend for patients with increases in CD8 T-cell infiltration in on-treatment biopsies to demonstrate greater anti-tumor efficacy. Further, there is evidence of a correlation between exposure, T cell infiltration, and response to provide further support for the higher dose exploration.

- Of the 165 patients (Part I only) treated with NIR178 160mg twice daily continuously in combination with PDR001 400mg every 4 weeks, 99 patients (60.0%) experienced AEs (all grades) suspected to be related to study treatment. The most commonly reported AEs were fatigue (29 patients, 17.6%), increased AST (20 patients, 12.1%), decreased appetite (17 patients, 10.3%), increased ALT (16 patients, 9.7%), nausea (15 patients, 9.1%), vomiting (10 patients, 6.1%), pruritus (9 patients, 5.5%). For further details, please refer to the [NIR178 (PBF-509) Investigator's Brochure].
- Exposure-response analysis for safety indicates that the steady-state pharmacokinetic exposure of NIR178 at 240 mg BID combined with PDR001 400 mg Q4W is below the select 33% probability threshold for patients to develop Grade 3-4 AST and/or ALT elevation. Further, preliminary analysis revealed a concentration-dependency in hepatotoxicity AEs across the clinically relevant exposure range of NIR178. Despite the positive trend of AST/ALT elevations with exposure, elevation of transaminases was in general reversible and manageable upon dose reduction or interruption based on clinical observation. Therefore, existing guidelines in the protocol for dose reduction and/or interruption for NIR178 are considered to be effective in managing transaminase elevations by decreasing drug exposure (refer to [Table 6-2](#)).
- NIR178 240 mg BID + PDR001 400 mg Q4W was determined to be the maximum tolerated dose (MTD) for the double combination and was well tolerated in patients with advanced NSCLC. Increasing the dose of NIR178 to 240 mg BID from 160 mg BID will add one additional dose reduction step if needed, as follows: 240 mg (starting dose), 160 mg (dose level -1, 33% reduction), 120 mg (dose level -2, 25% reduction), and 80 mg (dose level -3, 33% reduction). Dose reduction below 80 mg BID is not allowed (refer to [Table 6-5](#)).

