4.1.2 Part 2: NIR178+PDR001 schedule optimization

Part 2 of the study will enroll only patients with advanced/metastatic NSCLC who are naïve to prior immunotherapy. Eligible patients will be randomized in a 1:1:1 fashion to one of 3 groups, each evaluating a different dosing schedule of NIR178 within a 28 day cycle ([Figure 4-3](#)). The dosing schedule of PDR001 will be the same in each group (400mg IV every 28 days). Randomization will be done in order to balance covariates across the three different groups. Given the known correlation between PD-L1 expression and response to PD-1 inhibitors in NSCLC, the treatment groups will be analyzed retrospectively according to baseline PD-L1 expression (present/absent) defined by expression levels $<1\%$ or $>1\%$ by immunohistochemistry (IHC).

Three schedules of NIR178 will be evaluated in parallel in combination with PDR001 (Figure 4-3):

- NIR178 S1: BID continuous
- NIR178 S2: BID 14 days on/14 days off
- NIR178 S3: BID 7 days on/7 days off

Figure 4-3 Alternate NIR178 dosing schedules within one cycle

	Week 1							Week 2							Week 3							Week 4							
Day	1	2	3	4	5	6	7	1	2	3	4	5	6	7	1	2	3	4	5	6	7	1	2	3	4	5	6	7	
NIR178 S1	■	■	■	■	■	■	■	■	■	■	■	■	■	■	■	■	■	■	■	■	■	■	■	■	■	■	■	■	■
NIR178 S2	■	■	■	■	■	■	■	■	■	■	■	■	■	■															
NIR178 S3	■	■	■	■	■	■	■								■	■	■	■	■	■	■	■							

Each NIR178 dosing group will enroll 20 patients (total 60 patients). The safety, tumor response rates, and tumor immune modulation of the intermittent NIR178 schedules (NIR178 S2 and S3) will be compared to that in the continuous schedule (NIR178 S1). Based on cumulative data (including safety, tolerability, preliminary anti-tumor activity, PK, and PD) across the three schedules, an intermittent dosing schedule may be selected by Novartis for further evaluation in Part 3 of the study after documented discussion with study investigators.

[figure not shown]

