6.1.1 Dosing regimen

Treatment cycle is defined as 28 days.

In Part 1 of the study, all patients will receive NIR178 240 mg twice daily continuously and 400 mg of PDR001 administered every 28 days (prior to Amendment 5, all patients were treated with NIR178 160 mg BID).

In Part 2 of the study, all patients will be randomly assigned to one of the three NIR178 dosing schedules in combination with PDR001:

1. NIR178 S1: Patients will take NIR178 160mg twice daily continuously with PDR001 400mg administered once on day 1, every 28 days.
2. NIR178 S2: Patients will take NIR178 160mg twice daily on days 1-14 of a 28 day cycle together with PDR001 400mg administered once on day 1 every 28 days.
3. NIR178 S3: Patients will take NIR178 160mg twice daily on days 1-7 and days 15-21 of a 28 day cycle together with PDR001 400mg administered once on day 1 every 28 days.

In Part 3 of the study, one or two tumor groups may be selected based on emerging data from Part 1 and Part 2.

As of protocol amendment 6, Part 3 will be opened in parallel with Part 1 to further assess TNBC patients with a PD-L1 SP-142 status of IC=0 (<1%) using NIR178 FCT formulation continuous dosing schedule in combination with PDR001. A second tumor group may be considered for Part 3 after completion of Part 1. The first 10 patients enrolled in Part 3 will receive a NIR178 dose of 160 mg BID FCT, and after all patients complete at least 1 cycle of treatment, safety and PK analysis will be performed to decide whether the dose should be increased to NIR178 240 mg BID FCT. If there is unexpected toxicity due to formulation change the dose will not be escalated to NIR178 240mg BID FCT and an additional 10 patients will be enrolled at NIR178 160mg BID FCT. If the NIR178 160mg BID FCT formulation is considered safe, dose escalation to NIR178 240 mg BID FCT will occur and an additional 20 patients will be enrolled.

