Day of cycle				1	2	8	14	15	22	1	15	1	15					
Creatinine clearance	D	7.2.2.5.2.	X	X														
Hepatitis testing	D	7.2.2.5.5.	X															
HIV testing	D	7.2.2.5.5.	X															
Urinalysis (microscopic or macroscopic)	D	7.2.2.5.8.	X	If Clinically indicated														
Pregnancy test	D	7.2.2.5.7.	X	X						X		X		X	X	X		
Disease assessment/Tumor evaluation per iRECIST, RECIST v 1.1 or Cheson et al (2014) for lymphoma, color photography of visible lesion(s)	D	7.2.1.	X									Every 8 weeks from C1D1 for 40 weeks and every 12 weeks thereafter until progression of disease per iRECIST or Cheson et al (2014) or patient withdrawal			X (If not performed within 30 days prior to EOT)			
12 lead ECG	D	7.2.2.7.	X	X			X			X		X		X	X			
Adverse events	D	8.	X	Throughout the study											X	X		
NIR178 dosing	D	6.1.		As per assigned schedule														
PDR001 infusion	D	6.1.		X						X		X		X				

Visit Name	Category	Protocol Section	Screening	Cycle 1						Cycle 2		Cycle 3		Day 1 of Subsequent cycles	End of study treatment (EoT)	Follow up *
				1	2	8	14	15	22	1	15	1	15			
PK sampling for NIR178, NJI765 and PDR001	D	7.2.3.		X	X	X	X	X	X	X		X	X	X (up to cycle 6)	X	

*Please refer to Section 7.1.5 for safety follow up, Section 7.1.6 for disease progression follow up, Section 7.1.7 for survival follow up and Section 7.1.8 for information on lost to follow-up patients.
 
a: An optional tumor sample may be collected at disease progression when patients continue on study treatment due to overall clinical benefit.
																

[figure not shown]
[figure not shown]
[figure not shown]

Table 7-3 Visit evaluation schedule for patients in Part 2 NIR178 S3 (NIR178 Schedule 3-one week on, one week of dosing)

[figure not shown]
Visit Name	Category	Protocol Section	Screening	Cycle 1						Cycle 2		Cycle 3		Day 1 of Subsequent cycles	End of study treatment (EoT)	Follow up *	
				1	2	7	8	15	22	1	15	1	15				
Obtain Informed Consent	D	7.1.1.	X														
IRT Registration	D	6.4, 7.1.1.1.	X														
Demography	D	7.1.1.3.	X														
Inclusion/exclusion criteria	D	5.2, 5.3.	X														
Medical History	D	7.1.1.3.	X														
Smoking history	D	7.1.1.3.															
Diagnosis and extent of cancer	D	7.1.1.3.	X														
Prior antineoplastic therapy	D	7.1.1.3.	X														
Prior/concomitant medications	D	7.1.1.3.	X	Throughout the study										X	X		

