2.6.2.5 Laboratory data

Grading of laboratory values will be assigned programmatically as per CTCAE version 4.03. The calculation of CTCAE grades will be based on the observed laboratory values only, clinical assessments will not be taken into account.

CTCAE Grade 0 will be assigned for all non-missing values not graded as 1 or higher. Grade 5 will not be used.

For laboratory tests where grades are not defined by CTCAE 4.03, results will be categorized as low/normal/high) based on laboratory normal ranges.

The following summaries will be produced for hematology and biochemistry laboratory data (by laboratory parameter and treatment):

- Worst post-baseline CTC grade (regardless of the baseline status). Each patient will be counted only for the worst grade observed post-baseline;
- Shift tables using CTC grades to compare baseline to the worst on-treatment value;
- For laboratory tests where CTC grades are not defined, shift tables using the low/normal/high/(low and high) classification to compare baseline to the worst on-treatment value;

The following listing(s) will be produced for the laboratory data:

- Listing of all CTC grade 3 or 4 laboratory toxicities.

Liver function parameters

Liver function parameters of interest are total bilirubin (TBL), ALT, AST, and alkaline phosphatase (ALP). The number (%) of patients with worst post-baseline values as per Novartis Liver Toxicity guidelines will be summarized:

The following summaries will be produced:

- ALT or AST > 3xULN
- ALT or AST > 5xULN
- ALT or AST > 8xULN
- ALT or AST > 10xULN
- ALT or AST > 20xULN
- TBL > 2xULN
- TBL > 3xULN
- ALT or AST > 3xULN & TBL > 2xULN
- ALT or AST > 3xULN & TBL > 2xULN & ALP < 2xULN (*potential Hy's law*)

Potential Hy's Law events are defined as those patients with concurrent occurrence of AST or ALT > 3xULN and TBL > 2xULN and ALP < 2xULN in the same assessment sample during the on-treatment period. Further medical review should be conducted to assess potential confounding factor such as, liver metastases, liver function at baseline etc.

For more details and adaptation of above summary, Oncology Hepatic Safety guidance should be referred.

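### In Part 2, scheduled liver chemistry is on drug in S1 but follows a 7-day off-week in S3, so short-lived transaminase rises are likely under-counted in S3 and the by-schedule laboratory tables do not allow for it

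*Protocol*

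**What the plan says.** Protocol 6.1.1 sets the three Part 2 schedules:

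- S1: "NIR178 S1: Patients will take NIR178 160mg twice daily continuously with PDR001 400mg"
- S2: "NIR178 S2: Patients will take NIR178 160mg twice daily on days 1-14 of a 28 day cycle"
- S3: "Patients will take NIR178 160mg twice daily on days 1-7 and days 15-21 of a 28 day cycle"

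Tables 7-1 (S1), 7-2 (S2) and 7-3 (S3, "Visit evaluation schedule for patients in Part 2 NIR178 S3 (NIR178 Schedule 3-one week on, one week of dosing") place chemistry on identical days: screening, Days 1 and 15 of Cycles 1-3, Day 1 of each later cycle, and EoT. Other assessments were fitted to the dosing pattern. S3 has its ECG series on C1D7 (Table 7-7) and its PK profile on C1D7-8 (Table 7-11); S2 has the equivalents on C1D14-15. S3 patients also attend on C1D22. None of the S3 visits on C1D7, C1D8 or C1D22 carries chemistry.

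On the comparison, Protocol 4.1.2 states: "The safety, tumor response rates, and tumor immune modulation of the intermittent NIR178 schedules (NIR178 S2 and S3) will be compared" with S1. SAP 1.1.2 repeats this, and SAP 2.1 presents all Part 2 outputs by dosing schedule. SAP 2.6.2.5 then gives worst post-baseline grade, "Shift tables using CTC grades to compare baseline to the worst on-treatment value", and counts of patients above multiples of ULN for ALT/AST (>3, >5, >8, >10, >20) and bilirubin. Time since the last NIR178 dose plays no part in these summaries.

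On the liver signal, Protocol 2.3 reports a preliminary finding that hepatotoxicity depends on concentration, and says that "elevation of transaminases was in general reversible and manageable upon dose reduction or interruption based on clinical observation".

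**The concern.** If a rise depends on exposure and recedes when dosing stops, the timing of the blood draw relative to dosing affects whether it is recorded. S1 is measured under exposure and S3 at the end of each drug-free week. A lower rate of raised ALT/AST in S3 could then reflect the sampling calendar as much as the schedule.

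This is a main toxicity of the drug. Protocol 2.3 gives related AST increase in 20 of 165 Part 1 patients (12.1%) and ALT increase in 16 (9.7%) at 160 mg BID continuous. Protocol 1.2.1.4 lists Grade 3 ALT/AST increase among the dose-limiting toxicities, both alone and with PDR001.

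The effect also reaches beyond the laboratory tables. Under Protocol 8.1.1 a laboratory value becomes an adverse event only if it is clinically significant, causes signs or symptoms, needs therapy, or changes study medication. An asymptomatic rise that is never sampled also drops out of the AE and dose-interruption summaries.

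**Working it through.** **Off-period length.** SAP 2.4.1.1 defines it as cycle length minus planned treatment days. S3 (14-day sub-cycle): 14 - 7 = 7 days. S2: 28 - 14 = 14 days. This agrees with the SAP's own figures.

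**Drug-free days before each scheduled post-baseline sample.** Full days without NIR178 immediately before the nominal visit, from the dosing days in Protocol 6.1.1 and the chemistry rows of Tables 7-1 to 7-3:

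| Sample | S1 | S2 | S3 |
|---|---|---|---|
| C1D15 | 0 | 0 | 7 |
| C2D1 | 0 | 14 | 7 |
| C2D15 | 0 | 0 | 7 |
| C3D1 | 0 | 14 | 7 |
| C3D15 | 0 | 0 | 7 |
| C4D1 | 0 | 14 | 7 |
| C5D1 | 0 | 14 | 7 |
| C6D1 | 0 | 14 | 7 |
| Samples with 0 drug-free days | 8/8 | 3/8 | 0/8 |

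Screening and C1D1 are pre-treatment in every arm. EoT is not tied to a dosing phase; Protocol Appendix 2 (14.2.30) puts it within 14 days of last treatment.

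**Visit window.** Protocol 7.1 allows +/-3 days. An S3 sample 3 days early has 7 - 3 = 4 drug-free days before it; 3 days late, it has 3 days back on drug. An S2 Day 15 sample 3 days late has 3 drug-free days. S1 stays at 0 throughout.

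**What an S3 sample would show.** The documents give no recovery time, so this step rests on an assumption: baseline is 1xULN and the excess above it halves every h days off drug. The reading after 7 days is 1 + (P - 1) x 2^(-7/h) for a peak of P x ULN. For P = 5.1, just inside the SAP's >5xULN row:

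- h = 2: 1 + 4.1 x 0.088 = 1.4xULN
- h = 4: 1 + 4.1 x 0.297 = 2.2xULN
- h = 7: 1 + 4.1 x 0.5 = 3.05, about 3.1xULN

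For a reading above 3xULN after the off-week, the peak must exceed 1 + 2 x 2^(7/h): about 23.6, 7.7 or 5xULN for h = 2, 4 or 7. For a reading above 5xULN it must exceed 1 + 4 x 2^(7/h): about 46, 14.5 or 9xULN.

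**Context at the planned size.** With 20 patients per schedule and the Part 1 AST rate, the chance of at least one case is 1 - (1 - 20/165)^20 = 0.92. A two-sided 5% normal-approximation comparison of 12.1% with about 0% at 20 per arm has about 36% power. No formal safety test is planned, so these tables will be read by eye.

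**The case against.** The strongest case against the point is that detection is reduced but not removed, and that no decision now depends on it.

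- Rises lasting beyond a week are still recorded; with a 7-day half-time even the 5.1xULN example stays above 3xULN. All arms receive PDR001, and Protocol 6.2.1 allows immune-related events up to 12 weeks to recover under immunosuppression, so immune hepatitis need not clear in a NIR178 off-week.
- Protocol 7.2.2.5 allows extra tests when clinically indicated or at the investigator's discretion, so unscheduled detection is not confined to symptomatic patients. Table 6-2 recommends at least weekly liver tests for one cycle when NIR178 is resumed after a Grade 2 or 3 rise. EoT samples and the visit window add some on-drug values.
- S1 does not capture everything either: it is sampled two-weekly, then four-weekly from Cycle 4.
- Part 2 is closed. Protocol 2.2 gives efficacy as the reason for choosing continuous dosing, and any bias favours the schedules not chosen.

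All of this stands, and it limits the claim. A reader might infer that the plan cannot detect reversible rises under intermittent dosing at all. The documents do not support that: S2 has three scheduled samples directly after 14 dosing days, and S3 retains the routes above. A reader might also try to state what share of events is missed; with no recovery time or event distribution, none can be derived. Nor do the documents suggest that the choice of schedule was distorted.

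The objection does not remove the asymmetry in scheduled sampling. Unscheduled tests and post-rise monitoring depend largely on something having been noticed, and the +/-3 day window does not equalise the arms.

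**Conclusion.** The point holds as a limitation on interpretation. At nominal days, no scheduled post-baseline S3 chemistry sample before EoT directly follows dosing, against all of them in S1 and Day 15 of Cycles 1-3 in S2. From Cycle 4, S2 is sampled only after 14 days off. Rises that resolve within about a week are likely to be under-counted in S3 relative to S1, and partly in S2, and SAP 2.6.2.5 does not account for this.

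The direction rests on the protocol's own description of the rises as generally reversible and, on preliminary analysis, concentration-dependent. The size is unknown, and the 1.4 to 3.1xULN range depends wholly on the assumed half-times. The plasma half-life in Protocol 1.2.1.4.1 describes drug elimination and does not supply a recovery time for ALT or AST.

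The stakes are reduced because Part 2 is closed and the schedule was chosen on efficacy. What remains is that the study report could present lower S3 transaminase rates as a schedule effect. The SAP amendment made before final database lock already corrected Part 2 exposure for off-days; laboratory ascertainment needs the same recognition.

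**What to change.** In SAP 2.6.2.5, for Part 2 (by amendment, or by addendum if the database is locked):

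1. Keep the all-sample worst-grade, shift and ALT/AST tables, labelled as descriptive.
2. Add a supplementary ALT, AST and bilirubin table classifying each sample by planned dosing phase: the number of planned NIR178 dosing days in the preceding 7 days, not counting a dose on the sampling day. At nominal visits this is 7 for S1, 7 for S2 Day 15, 0 for S2 Day 1 from Cycle 2, and 0 for post-baseline S3 Days 1 and 15. Excluding the sampling-day dose matters because S3 restarts on Days 1 and 15, and a sample drawn just after restart would otherwise count as on drug.
3. Compare S2 with S1 at the matched Day 15 visits of Cycles 1-3. Keep values taken during AE-related holds; dropping them would select on the outcome.
4. State that S3 has no scheduled end-of-on-week chemistry before EoT, so lower laboratory toxicity for S3 than for S1 cannot be concluded from these tables.

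The cost is one derived variable and one extra table set. The matched comparison uses fewer samples per patient, and S3 gets an explicit limit rather than a corrected estimate. No new data are needed.

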7.1.1 Screening

The IRB/IEC study approved informed consent form (ICF) must be signed and dated before any study-specific screening procedure is performed. Procedures which are part of the clinical routine during the initial diagnostic work-up of the patient may be obtained before obtaining the ICF. A copy of the ICF must be given to the patient or to the person signing the form. The investigator or designee must record the date when the study informed consent was signed in the medical records of the patient.

Patients will be evaluated against study inclusion and exclusion criteria and safety assessments. For details of assessments, refer to [Table 7-1](#), [Table 7-2](#) and [Table 7-3](#). Screening assessments must be completed within 21 days prior to the first dose of treatment except for the radiological tumor assessment which should be performed within 28 days prior to the first dose. Screening assessments must be repeated if outside of screening windows. Patients are allowed to re-screen after abnormal labs or symptoms are corrected or treated.

Submission of a newly obtained tumor sample (formalin fixed, in ethanol) is required from all patients (except for patients in Japanese safety run-in part) at screening, unless the patient has a recently obtained tumor sample that meets the following criteria (both criteria must be met):

- Biopsy sample was collected \leq 6 months before 1st dose of study medication and the sample is available at the site.
- No immunotherapy was given to the patient since collection of biopsy sample.

For details refer to [Section 7.2.4](#).

7.1.1.1 Eligibility screening

Following registering in the IRT (except for Japanese safety run-in patients) for screening, patient eligibility will be checked once all screening procedures are completed. Please refer and comply with detailed guidelines in the IRT manual.

7.1.1.2 Information to be collected on screening failures

Patients who sign an informed consent but fail to be started on treatment for any reason will be considered a screen failure. The reason for not being started on treatment will be entered on the Screening Phase Disposition Page. The demographic information, informed consent, and Inclusion/Exclusion pages must also be completed for Screen Failure patients. No other data will be entered into the clinical database for patients who are screen failures, unless the patient experienced a Serious Adverse Event during the Screening Phase (see [Section 8](#) for SAE reporting details). If the patient fails to be randomized, the IRT must be notified within 2 days of the screen fail that the patient was not randomized.

7.1.1.3 Patient demographics and other baseline characteristics

Data to be collected will include general patient demographics, relevant medical history and current medical conditions, smoking history, diagnosis and extent of cancer, details of prior anti-neoplastic treatments, prior medication, procedures, significant non-drug therapies, baseline tumor molecular characteristics and any other assessments that are done for the purpose of determining eligibility for inclusion in the study.

7.1.2 Treatment period

The treatment period commences on the first day of the first cycle of NIR178 and PDR001 combination.

During the study treatment period, patients will be regularly monitored to assess the safety and early anti-tumor activity of treatment. For purpose of scheduling and evaluations, a treatment cycle will consist of 28 days.

Patients who meet the following criteria **should continue treatment** in additional cycles:

- Patients who do not have a PD per iRECIST ([Appendix 3](#)) or [Cheson et al 2014](#) (DLBCL), (and/or progressive disease per PCWG3 guidance ([Appendix 5](#)) for mCRPC).

Patients who meet the following criteria **might continue treatment** in additional cycles:

- Patients with confirmed PD per iRECIST ([Appendix 3](#)) or [Cheson et al 2014](#) (DLBCL), (and/or progressive disease per PCWG3 guidance ([Appendix 5](#)) for mCRPC), if the Investigator considers it to be in the patient's best interest to remain on the study, and after documented discussion with the Novartis medical monitor.

Patients who meet the following criteria **will NOT continue treatment** in additional cycles:

- Patients who experience unacceptable toxicity.
- Rapid disease progression or threat to vital organs or critical anatomical sites [e.g., CNS metastasis, respiratory failure due to tumor compression, spinal cord compression] requiring urgent alternative medical intervention; significant, unacceptable or irreversible toxicities related to study treatment.
- Patients with confirmed PD per iRECIST ([Appendix 3](#)) or [Cheson et al 2014](#) (DLBCL), (and/or progressive disease per PCWG3 guidance ([Appendix 5](#)) for mCRPC) unless they meet the criteria above for continuation of treatment. These patients will then enter the Safety follow-up period.
- Patients with an unconfirmed PD per iRECIST who show signs of clinical deterioration or toxicity. These patients will enter the Safety follow-up period, and will continue to be followed-up until confirmed irPD or initiation of a new treatment.

Clinical experience indicates that objective responses to immunotherapy follows delayed kinetics of weeks or months, and can be preceded by initial apparent radiological progression or appearance of new lesions or some enlarging lesions while other target lesions are regressing ("mixed response") ([Wolchok et al 2009](#)). It is therefore reasonable to allow for these possibilities and continue to treat the patient until progression is confirmed and found to be advancing at the next imaging assessment as per iRECIST. An outline of the iRECIST is provided in [Appendix 3](#).

These considerations should be balanced by clinical judgment as to whether the patient is clinically deteriorating and unlikely to receive any benefit from continued treatment.

Such deterioration will be assessed to have occurred after a clinical event that, in the Investigator's opinion, is attributable to disease progression, is unlikely to reverse with continued study treatment and therefore indicates that the patient is not benefiting from study treatment and cannot be managed by the addition of supportive care.

During the treatment period, the patient is obliged to follow the investigators instructions with regards to contraception, concomitant medications and dosing regimen. There is no fixed duration; patients may continue treatment with the study drug until the development of an unacceptable toxicity that precludes any further treatment, disease progression, and /or treatment is discontinued at the discretion of the Investigator or by patient refusal. For details of assessments during the treatment period, refer to [Table 7-1](#), [Table 7-2](#) and [Table 7-3](#).

